14.2 General statistical considerations

Summary statistics will consist of frequency tables for categorical variables. For continuous variables, summary statistics will consist of number of available observations, arithmetic mean, SD, median, minimum, and maximum unless stated otherwise.

All statistical tests will be performed 2-sided at a 5% level of significance unless stated otherwise.

14.3 Planned efficacy analyses

14.3.1 Analysis of the primary and secondary efficacy variables

A fixed sequence testing procedure will be applied for the primary and selected secondary variables. The testing procedure will control the family-wise type-I-error and will account for multiplicity. The family-wise error will be set to $\alpha=0.05$ (2-sided).

For each test, on each binary efficacy endpoint, the null hypothesis is that the conditional odds ratio is equal to one.

$$H_0: OR_{T1T2} = 1$$

The alternative hypothesis is that the conditional odds ratio is not equal to one.

$$H_A: OR_{T1T2} \neq 1$$

For each test, on each continuous efficacy endpoint, the null hypothesis is that there is no difference between treatment groups.

$$H_0: T_1 - T_2 = 0$$

The alternative hypothesis is that there is a difference between treatment groups.

[figure not shown]
$$H_A: T_1 - T_2 \neq 0$$

For the primary and secondary variables, the primary comparison is the bimekizumab 160mg sc Q4W vs placebo. Point estimates and 95% confidence intervals (CI) will be calculated.

The testing starts with H_1 . If H_1 can be rejected at $\alpha=0.05$ (2-sided), the corresponding α will be passed on to the next test in the sequence and testing will continue. The testing will be stopped if a hypothesis cannot be rejected at $\alpha=0.05$ (2-sided).

The fixed sequence testing procedure of primary and secondary efficacy endpoints is shown in [Figure 14-1](#).

Figure 14-1: Sequential testing procedure of primary/secondary efficacy endpoints (fixed sequence testing procedure)

ACR50=American College of Rheumatology 50% response criteria; BKZ=bimekizumab; CfB=change from Baseline; H=hypothesis; HAQ-DI=Health Assessment Questionnaire-Disability Index; MDA=Minimal Disease Activity; PASI90=Psoriasis Area and Severity Index 90; PCS=Physical Component Summary; Q4W=every 4 weeks; SF-36= Short-Form 36-item Health Survey; W=Week

14.3.1.1 Analysis of the primary efficacy variable

The primary efficacy variable will be analyzed for all subjects in the RS.

The primary endpoint is the ACR50 response at Week 16. The primary efficacy analysis will evaluate the composite estimand in the RS. The composite estimand combines the clinically meaningful improvement from Baseline in ACR50 response and not discontinuing treatment early. This composite estimand is similar to nonresponder imputation (NRI).

The following 4 attributes describe the estimand that will be used to define the treatment effect of interest for the primary efficacy analysis:

1. Population = Subjects enrolled according to the protocol-specified inclusion/exclusion criteria and randomized to IMP
2. Subject-level outcome = ACR50 at Week 16
3. Intercurrent event handling = An intercurrent event is defined as discontinuation of study treatment prior to Week 16. A composite strategy will be implemented in which a positive clinical outcome is defined as achieving ACR50 at Week 16 and not discontinuing study treatment through Week 16.
4. Population-level summary measure = Conditional odds ratio comparing bimekizumab to placebo.

As the ACR response is based on 7 different component scores, it is necessary to consider various data scenarios that could impact the calculation of response. The rules described here are applicable in the context of the calculation of ACR response and may differ from the rules applied for calculating and summarizing the components individually (some values may need to be imputed for component analysis but are not required here to evaluate ACR response).

The following rules will be applied prior to invoking any imputation analysis at the variable level:

- If a subject has a component value that is equal to 0 at Baseline and the post-Baseline value is greater than or equal to 0, then the percent improvement for that component will be treated as 0 for purposes of ACR response calculations.
- If a subject has component values that are missing at Baseline, then the percent improvement for that component will be treated as missing for purposes of ACR response calculations

Observed data will be used to calculate ACR response where possible. In case of partial missing data where an observed response may be calculated, imputed data will not change the result.

Missing data at Week 16 that are not preceded by an intercurrent event, and any data after an intercurrent event will be imputed as nonresponders.

The statistical hypothesis for the ACR50 response at Week 16 is that the conditional odds ratio for ACR50 response in the bimekizumab treatment compared with placebo is equal to 1.

A logistic regression model will be used to assess the treatment effect on ACR50 response at Week 16. The model will include fixed effects for treatment. The suitability of including the randomization stratification variables, prior TNF α exposure and region will be assessed, and will be added to the model if appropriate. Comparisons will be made using the 2-sided Wald test at a significance level of $\alpha=0.05$ (ie, H₁ [Figure 14-1](#)). The odds ratio vs placebo, p-value and the 95% CI will be calculated.

Any use of prohibited or rescue medications through Week 16 would constitute an important protocol deviation which would be accounted for when the sensitivity analysis based on the PPS is performed (see Section [14.3.1.1.1](#)).

14.3.1.1.1 Supportive analyses

Supportive analyses for the primary efficacy variable will be conducted:

1. The analysis will be repeated based on the PPS to evaluate the effect of important protocol deviations on the analysis.
2. The analyses will be repeated for all subjects in the FAS to evaluate the consistency between the RS and the more restrictive FAS. This analysis will only be performed if the number of subjects in RS and FAS are different.
3. The primary comparison will also be repeated for all individual components of the ACR50 response to explore the effect of the signs and symptoms of the individual components on the composite endpoint. Since all ACR components are continuous variables (eg, change from Baseline in TJC), an analysis of covariance (ANCOVA) with treatment, prior TNF α exposure and region, as fixed effects and the Baseline value as covariate will be used for the analysis. Note as outlined above, some additional values may need to be imputed for component analysis which are not required to evaluate the overall ACR response.
4. The analysis will be repeated using a modified composite estimand where intercurrent events are defined only as discontinuation due to AE or lack of efficacy.
5. The analysis will be repeated using a treatment policy approach.

6. The analysis will be repeated using observed cases only.
7. The analysis will be repeated using the COVID-free Set.

Additional sensitivity and supportive analyses to evaluate varying assumptions related to the handling of missing data will also be performed and are described in [Section 14.7](#).

14.3.1.2 Analyses of the secondary efficacy variables

The secondary efficacy variables will be analyzed for all subjects in the RS.

All binary variables that are part of the testing hierarchy are given below:

- PASI90 responders at Week 16 will be analyzed to evaluate the composite estimand. The composite estimand combines the clinically meaningful improvement from Baseline in PASI90 response and not discontinuing treatment early.
- The proportion of subjects achieving MDA status at Week 16 will be analyzed to evaluate the composite estimand. The composite estimand combines (1) achieving the MDA status with (2) not discontinuing treatment early.

The statistical hypothesis for the binary variables at Week 16 is that the conditional odds ratio for binary variable in the bimekizumab treatment compared with placebo groups is equal to 1.

The binary variables will be analyzed using the same analysis methods as used for the primary variable ([Section 14.3.1.1](#)).

All continuous variables that are part of the testing hierarchy are given below:

- Change from Baseline in HAQ-DI at Week 16.
- Change from Baseline in SF-36 PCS score at Week 16.

Continuous variables will be analyzed to evaluate the hypothetical estimand as defined below:

1. Population = Subjects enrolled according to the protocol-specified inclusion/exclusion criteria and randomized to IMP
2. Subject level outcome = variable as stated in [Section 4.2.1](#)
3. Intercurrent event handling = An intercurrent event is defined as discontinuation of study treatment prior to Week 16. A hypothetical strategy for addressing intercurrent events will be implemented. This estimand targets the treatment difference in a scenario where withdrawal from study treatment does not occur, such that outcomes for subjects without an intercurrent event are as observed, and outcomes for subjects with an intercurrent event are treated as though they had completed the randomized study treatment through Week 16. A multiple imputation strategy will be used to impute data following an intercurrent event.
4. Population-level summary measure = the difference in the adjusted means between bimekizumab 160mg Q4W and placebo.

Any missing data at Week 16 that is not preceded by an intercurrent event (ie, discontinuation of study medication) will also be imputed based on a predefined MI model. In MI, the missing value is replaced by a set of plausible values, where each value is a Bayesian draw from the conditional distribution of the missing data given the observed data. Intermittent missing data

will be imputed using the MCMC method, followed by monotone regression for monotone missing data.

The statistical model for continuous endpoints for the comparison of bimekizumab and placebo will be an ANCOVA model with treatment, prior TNF α exposure and region as fixed effects and the Baseline value as covariate. The statistical hypothesis for the continuous variables at Week 16 is that the treatment difference between the bimekizumab treatment group and placebo is equal to 0.

All secondary efficacy variables will also be summarized based on observed case data as well as multiple imputation using the modified composite estimand for binary variables.

Variables that are included in the hierarchy will additionally be rerun using the COVID-free Set.

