9.9 Minimal Disease Activity (MDA) and Very Low Disease Activity (VLDA)

Minimal Disease Activity and VLDA are states of disease activity deemed useful targets of treatment by both the subject and physician, given current treatment possibilities and limitations. Criteria covering all of the domains of the disease have been developed to determine whether or not a subject has reached MDA or VLDA based on key outcome measures in PsA (Mease, 2011; Coates et al, 2010).

A subject is considered as having MDA if 5 or more of the following 7 criteria are fulfilled:

- Tender joint count ≤ 1
- Swollen joint count ≤ 1
- PASI ≤ 1 or BSA ≤ 3
- Patient pain VAS ≤ 15
- PGA-PsA VAS ≤ 20
- HAQ-DI ≤ 0.5
- Tender enthesial points ≤ 1

A subject is considered as having VLDA if all 7 of the above criteria are fulfilled.

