14.9.1 Power calculation for primary endpoint

The sample size assumptions for bimekizumab vs placebo are based on the ACR50 response data in the subgroup of TNF α -IR patients from the Phase 2b bimekizumab study in a mixed prior TNF α therapy population of subjects with moderate to severe PsA (PA0008). Sample size calculations for a TNF α -IR population are also based on ACR50 responses at Week 16 in the SPIRIT-P2 study.

Observed ACR50 at Week 12 results in the PA0008 TNF α -IR populations were in a small number of subjects; bimekizumab 160mg (n=7), 320mg (n=8), and 320mg (initial dose) plus 160mg (n=8) and ranged from 14.3% to 37.5%.

The ixekizumab Phase 3 study SPIRIT-P2 is conducted on a similar patient population to that in this study and showed a 35% (n=122) ACR50 response at Week 16. Therefore, taking into account the range of ACR50 responses at Week 12 in PA0008, the estimated ACR50 response at Week 16 in the bimekizumab 160mg sc Q4W group is conservatively assumed to be 26%.

For placebo, a similar approach as above is used. In the PA0008 TNF α -IR population, an ACR50 response of 11.1% (n=9) was observed at Week 12. The observed placebo ACR50 response at Week 16 was less than 10% in the SPIRIT-P2 study (n=118). Therefore, the estimated ACR50 response at Week 16 in the placebo group is assumed to be 10%.

The sample size for showing statistical superiority of bimekizumab vs placebo was calculated using a 2-sided 2-sample Chi-square test with continuity correction (Fleiss et al, 1980).

Assuming 260 subjects in the bimekizumab group and 130 subjects in the placebo group, the test for detecting statistical superiority of bimekizumab 160mg vs placebo based on ACR50 response at Week 16 has 96% power to detect a true treatment difference of 16% (odds ratio of 3.16).

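### MDA at Week 16 is an absolute end state, but its model has no baseline severity term; one prespecified covariate would be a modest efficiency gain, not the repair of an error

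*Protocol*

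**What the plan says.** Section 14.3.1.2 lists MDA at Week 16 among the binary endpoints of the testing hierarchy, under a composite estimand, and sets its method by reference: "The binary variables will be analyzed using the same analysis methods as used for the primary variable".

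The method referred to is in section 14.3.1.1: "The model will include fixed effects for treatment". The only other terms contemplated are prior TNFα exposure and region, which enter only after an assessment: "The suitability of including the randomization stratification variables" is to be examined first. No measure of disease severity at Baseline is named.

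Section 9.9 defines the endpoint: "A subject is considered as having MDA if 5 or more of the following 7 criteria are fulfilled". The seven criteria are fixed levels, among them joint counts of at most 1 and HAQ-DI of at most 0.5. None is relative to the subject's own Baseline.

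The continuous hierarchy endpoints (HAQ-DI and SF-36 PCS) are treated differently. Their ANCOVA has treatment, prior TNFα exposure and "region as fixed effects and the Baseline value as covariate".

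**The concern.** ACR50 and PASI90 measure improvement relative to Baseline, so part of the starting level is built into them. MDA does not work that way. Some of its criteria can already be met at entry:

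- Inclusion criterion 5 requires at least 3 tender and 3 swollen joints, so both joint criteria fail at Baseline. Section 6.1 sets no minimum for pain, patient global, HAQ-DI, skin or entheses.
- Section 14.9.2 assumes that 50% of subjects have BSA of at least 3%. On that assumption about half start with the skin criterion met.
- Section 4.3.1 restricts the HAQ-DI responder analysis to subjects above 0.35 at Baseline, and the enthesitis analyses to subjects with enthesitis. It therefore allows for subjects who start below those limits.

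The ACR50 model has thus been carried over to an endpoint of a different kind. Two modest things are at stake: some power for a test in the hierarchy, and the exposure of the estimate to a chance difference in starting severity between the arms.

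**Working it through.** **Inputs.** From section 14.9: 260 vs 130 subjects; placebo MDA 5%; difference 12 points, hence 17% on bimekizumab; odds ratio 3.892; stated power 92%; chi-square test with continuity correction; two-sided 5% level. Not in the protocol: how strongly baseline severity predicts MDA. This is assumed, as an odds ratio per SD of 1 to 3.

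**1. The plan's own figure.** Odds ratio = (0.17/0.83)/(0.05/0.95) = 3.892.

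Let n be the placebo size, k = 2, d = 0.12 and p̄ = (0.05 + 2 × 0.17)/3 = 0.13.

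- Null term: 1.96 × √(0.13 × 0.87 × 1.5) = 0.807.
- Alternative term: √(0.05 × 0.95 + 0.17 × 0.83/2) = 0.344.
- Without correction: z = (0.12 × √130 − 0.807)/0.344 = 1.63, power 94.9%.
- With correction, 130 = (n/4)·[1 + √(1 + 2(1 + 1/k)/(nd))]² gives n = 117.8. Then z = (0.12 × √117.8 − 0.807)/0.344 = 1.44, power 92.5%.

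The stated 92% reproduces.

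**2. Expected events.** 260 × 0.17 + 130 × 0.05 = 44.2 + 6.5 = 50.7. One more continuous term is affordable. The 6.5 placebo events argue against a longer list.

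**3. Gain from adjustment.** Simulation with 4000 trials per setting, a logistic Wald test, one standard-normal baseline covariate, and marginal response rates held fixed. Power without → with the covariate:

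| Odds ratio per SD | 17% vs 5% | 15% vs 5% | 13% vs 5% |
|---|---|---|---|
| 1 (not prognostic) | 94.5 → 94.5 | 87.7 → 87.5 | 72.2 → 72.3 |
| 1.5 | 95.1 → 95.2 | 86.7 → 87.2 | 70.5 → 71.9 |
| 2 | 95.2 → 95.9 | 86.7 → 87.9 | 71.1 → 73.3 |
| 3 | 94.6 → 96.7 | 86.9 → 90.3 | 70.3 → 75.5 |

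Monte Carlo standard error is about 0.3 to 0.7 points per figure. The gain is about 0 to 2 points at the planned rates. A true rate of 14% lies between the last two columns, at about 0 to 5 points.

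**4. Type I error.** With 10% in both arms and odds ratios per SD of 1, 2 and 3, rejection is 4.9% to 5.1% without the covariate and 4.8% to 5.0% with it.

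**5. Chance imbalance.** The SE of the baseline difference is √(1/130 + 1/260) = 0.107 SD, so a 2-SE imbalance is 0.21 SD. The unadjusted log odds ratio then shifts by roughly 0.21 × ln 2 = 0.15, or 0.21 × ln 3 = 0.24 (0.215 before rounding). The SE of the log odds ratio is √(1/6.5 + 1/123.5 + 1/44.2 + 1/215.8) = 0.44. The shift is about 0.3 to 0.5 of that SE.

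**6. Effect on the odds ratio.** With response rates held at 17% and 5%, the conditional odds ratio is 3.97, 4.14 and 4.58 for odds ratios per SD of 1.5, 2 and 3, against 3.89 without adjustment.

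**The case against.** The strongest reply is that nothing here is wrong. An unadjusted or stratification-adjusted logistic test is standard, and randomization already accounts for chance imbalance in its error rate. Step 4 confirms this, and the point stands in full.

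The gain is also small where it can be tied to the protocol's own figures. At an odds ratio per SD of 1.5 it is about 0.1 points at the planned rates. Larger gains need a smaller true effect and a stronger covariate, and the protocol gives no figure for either. The simulated covariate is idealised: normal, and linear in the log odds. HAQ-DI is one of seven criteria and need not behave that way. This stands as a limit on the size of the claim.

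The ANCOVA comparison is imperfect. There the covariate is the endpoint's own Baseline value, whereas a binary status has no direct counterpart, so a proxy must be chosen. That is a reason to name one covariate in advance.

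Two costs are real. The odds ratio changes meaning. And section 14.3.1.2 analyses the Randomized Set, while section 14.1 requires valid Baseline components only for the Full Analysis Set, so a Baseline covariate could drop randomized subjects unless a rule covers them. Against the first, section 14.3.1 already frames the binary hypotheses as conditional odds ratios.

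A statistical analysis plan may add detail, but the protocol text does fix the MDA method as that of ACR50.

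**Conclusion.** The point holds as an efficiency improvement of low priority. MDA is an absolute state in the confirmatory hierarchy, and its model has no place for baseline severity. One prespecified covariate would gain about 0 to 2 points of power at 17% vs 5% and about 0 to 5 points near 14% vs 5%. It would also remove conditional bias from imbalance in starting severity. These figures rest on an assumed odds ratio of 1 to 3 per SD and on an idealised covariate.

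A reader might infer that the MDA test is biased, that its type I error is inflated, or that the trial is underpowered for MDA. The documents do not support any of these: the test keeps its size and the stated 92% reproduces. Nor is the added power strictly free, because the odds ratio is non-collapsible and its target changes.

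**What to change.** In section 14.3.1.2, before unblinding, prespecify Baseline HAQ-DI as the single additional covariate in the MDA logistic model, alongside treatment and whichever stratification factors are used. Table 5-1 already schedules HAQ-DI at Baseline for all subjects, so no new data are needed.

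Add a simple rule for randomized subjects without a Baseline HAQ-DI, for example imputing the overall mean across both arms, so that the full Randomized Set is kept. Retain the model without HAQ-DI as supportive.

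The cost is one model term and two or three sentences. The report should say that the MDA odds ratio is conditional on Baseline HAQ-DI and is expected to be somewhat larger than the planned 3.892 for the same response rates. Showing the response proportions beside it avoids misreading.

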14.3.2 Analyses of the other efficacy variables

All other efficacy variables will be analyzed for all subjects in the RS.

Generally, the estimand structure for binary other efficacy variables is as described below. Note that further details will be provided in the SAP.

1. Population = Subjects enrolled according to the protocol-specified inclusion/exclusion criteria and randomized to IMP.
2. Subject-level outcome = The given variable and time point being summarized (eg, ACR20 at Week 8)
3. Intercurrent event handling = An intercurrent event is defined as discontinuation of study treatment prior to the time point being summarized. A composite strategy will be implemented in which a positive clinical outcome is defined as achieving the given variable at the specified time point and not discontinuing study treatment through that time point.
4. Population-level summary measure = Unadjusted proportion of responders

Any missing data that are not preceded by an intercurrent event as described above will be imputed based on NRI as described for the primary and secondary efficacy variables.

Continuous variables will be summarized using descriptive statistics by treatment group and by each visit. Generally, the estimand structure for continuous other efficacy variables is as described below. Note that further details will be provided in the SAP.

1. Population = Subjects enrolled according to the protocol-specified inclusion/exclusion criteria and randomized to IMP
2. Subject-level outcome = The given variable and time point being summarized (eg, change from Baseline in HAQ-DI at Week 8)
3. Intercurrent event handling = An intercurrent event is defined as discontinuation of study treatment prior to the time point being summarized. A hypothetical strategy will be implemented in which outcomes for subjects without an intercurrent event are as observed at the given time point, and outcomes for subjects with an intercurrent event are treated as though they had completed the randomized study treatment through the time point being summarized. A multiple imputation strategy will be used to impute data following an intercurrent event.

4. Population-level summary measure = Unadjusted mean.

Any missing data that are not preceded by an intercurrent event as described above will be imputed based on a predefined multiple imputation model as described for continuous secondary efficacy variables.

Other binary and continuous efficacy variables will also be summarized based on observed case (OC) data (ie, subjects with missing data or who have prematurely discontinued study treatment are treated as missing). Further, binary outcomes will be summarized using the modified composite estimand.

The time to ACR20/50/70 response will be estimated and presented using the Kaplan Meier product limit method for each treatment. Time to a given response will be defined as the time in days from Baseline until the first date when the response is achieved. Subjects who discontinue study treatment prior to achieving a response will be censored at the date of study treatment discontinuation. The median time to response, including the 2-sided 95% CI, will be calculated for each treatment. Between group differences will be analyzed using a log-rank statistic.

The time to ACR20/50/70 endpoints will be analyzed using OC data. All other efficacy variables will be analyzed based on imputed and on OC data.

